#### **SECONDARY OUTCOMES**

- Change in insulin resistance from baseline on POD 2 and POD 3 measured using a technique called HOMA, which utilises serial fasting blood glucose and insulin measurements.
- Stress response following surgery, measured by sampling cortisol levels preoperatively, at the end of surgery, and at 24 hours post-operatively and the inflammatory response measured by CRP levels preoperatively, and on POD 1,2 and 3.
- Ultrasound measurement of gastric volume pre-operatively (see Appendices for technique)
- Recovery profile including:
  - PQRS (see Appendices) score measured pre-operatively, at 2 hours after surgery, POD 3 and POD 7;
  - Muscle strength measured using a grip strength dynamometer pre-operatively, twice daily (morning and afternoon) on POD 1, 2 and 3, and then once daily on alternate days thereafter until discharge (the patient's dominant hand will be used for this measurement, and the best out of three consecutive strengths will be used with mean values analysed);
  - Time to surgical fitness for discharge (see Appendices for criteria) measured in hours (date and time of fitness for surgical discharge is recorded in the ERP database).
- Morbidity measured using the POMS score on POD 2 and POD 5 (see Appendices).
- PONV VAS score on POD 1.
- Sensations of thirst & hunger VAS score immediately pre-operatively and on POD 1.
- Caloric intake POD 1 and 2.
- Ambulation time POD 1 and 2.
- Adverse events i.e. aspiration and hypo- or hyperglycaemia (these are the only relevant safety assessments for these interventions) will be assessed on the operative day for the former & up to the end of POD 1 for the latter.
- Cost analysis: difference in cost between doses of Pre-Load & Generation UCAN and costs of respective hospital and critical care lengths of stay.

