#### 5.6 Sample Size

The standard deviation for insulin resistance data was obtained from a previous study of pre-operative carbohydrate treatment in total hip replacement surgery (Soop 2001). Twenty patients in each group are needed based on 80% power for a two-sample t-test, detecting a minimal important difference of 15% in change of insulin resistance on the first postoperative day from baseline, with a standard deviation of 16% and a two-tailed significance level of 0.05. A minimal important difference of 25% was used in a previous study comparing pre-operative carbohydrate treatment with a placebo group for patients who had total hip replacement (Soop 2004) . In this study two carbohydrate drinks are being compared, PreLoad with Generation UCAN. Therefore, a smaller minimal important difference of 15% was deemed appropriate. This sample size calculation allows for 10% attrition.

\*\* Measured twice a day first three postoperative days then alternate days until discharge from hospital.

\*\*\*The baseline HOMA to be done on either of these 2 visits as long as the patient is fasted.

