#### 5.7 RECRUITMENT

The colorectal specialist nurses will be asked to forward details of patients listed for eligible surgery following each Colorectal Cancer MDT Meeting. All of the surgeons who are part of this group, along with the Waiting List Clerks who book the operation dates, the Pre-operative Assessment Clinic staff (the CI also undertakes weekly Cardiopulmonary Exercise Testing Clinics in this area) and the Enhanced Recovery Nurse will all be aware of the study eligibility criteria and inform the research team as early as possible regarding such patients.

Patients requiring admission to a higher level of care and therefore arterial line monitoring will be preferred due to the ease of blood sampling.

Local data for the past four years indicates an average of 50 eligible patients per year at the Royal Blackburn Hospital. The Royal Surrey County Hospital has a higher volume of eligible patients. Due to the non-invasive nature of the intervention and experience with current interventional RCT at both centres in a similar study population a high approach to consent ratio would be expected. Hence recruitment of 40 patients (20 patients per centre) is feasible in 6 months.

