## 7. METHODS: DATA COLLECTION, MANAGEMENT, AND ANALYSIS

#### 7.1 Data collection methods

Data will be collected from patient notes (pre-operative assessment booklet, anaesthetic chart, operative note, notes made post-operatively) and the ERP Database. The research team will perform the blood sampling and record the measured results as described and collect the VAS scores.

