## POST-OPERATIVE DATA COLLECTION

- POSSUM score from ERP Database
- Blood samples:
  - Fasting insulin (3 samples to be taken at 5 minute intervals and glucose on the morning of POD 1, 2 and 3
  - Cortisol (at end of operation and at 24 hours)
  - o CRP (POD 1 and 3)
- PQRS score Theatre Recovery, POD 3 and POD 7.
- PONV and Thirst and hunger sensation VAS scores on POD 1.
- POMS score on POD 2 and 5
- Hand grip strength measurement twice daily on POD 1, 2 & 3 and then alternate days until discharge
- Calories intake POD1 and POD2
- Ambulation time (minutes) POD1 and POD2
- MUAC POD5 or Day of Discharge if earlier
- Adverse Events up to end POD 1.
- Date and time reached surgical fitness for discharge and actual discharge obtained from ERP Database

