#### 7.3 STATISTICAL METHODS

#### STATISTICAL METHODS FOR ANALYSING PRIMARY AND SECONDARY OUTCOMES

Baseline demographic and clinical variables will be reported for the two groups using summary statistics. Categorical variables will be reported using frequencies and percentages. Quantitative variables will be reported using either the mean and standard deviation or the median and interquartile range depending on the skewness of the data

In terms of the primary outcome, the mean difference in change of insulin resistance from baseline to POD 1 will be compared using either the Independent Samples T-Test or Mann-Whitney U Test. This will depend on the skewness of the data distribution.

Between-group comparisons of quantitative secondary outcomes including change of insulin resistance from baseline to POD 3, the PQRS score and time to surgical fitness will made using either the Independent Samples T-Test or Mann-Whitney U Test, depending on the skewness of the distribution of the data. Categorical secondary outcomes will be compared between groups using the Chi-square test.

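### The critical care part of the cost outcome has no listed data item, and the general skewness rule does not suit a cost comparison

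*Protocol*

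**What the plan says.** Protocol section 5.4 closes its list of secondary outcomes with "Cost analysis: difference in cost between doses of Pre-Load & Generation UCAN and costs of respective hospital and critical care lengths of stay". Critical care stay is therefore a stated component of the outcome.

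Section 7.1 gives the general sources: "Data will be collected from patient notes (pre-operative assessment booklet, anaesthetic chart, operative note, notes made post-operatively) and the ERP Database". It then itemises what is recorded at the pre-operative assessment clinic, on the operative day and after surgery. The only item there that bears on length of stay is "Date and time reached surgical fitness for discharge and actual discharge obtained from ERP Database". None of the three lists has a critical care admission, discharge or day count. The timeline in section 5.5 has only a generic row for outcome data.

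Section 5.7 adds that "Patients requiring admission to a higher level of care and therefore arterial line monitoring will be preferred", for ease of blood sampling.

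Section 7.3 fixes the analysis. The rule opens with "Between-group comparisons of quantitative secondary outcomes including change of insulin resistance from baseline to POD 3", goes on to PQRS score and time to surgical fitness, and assigns the test as "Independent Samples T-Test or Mann-Whitney U Test, depending on the skewness of the distribution of the data". Cost is not named, and no separate method for it is given.

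**The concern.** There are two separate gaps.

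The first is in data capture. A component of a named outcome has no matching item in lists that otherwise go down to arm circumference, calories and minutes of ambulation. An analysis plan can only analyse what was collected, so the protocol is the place to settle this. Recruitment leans towards patients who need a higher level of care, so the component is unlikely to be negligible, although the protocol gives no proportion.

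The second is in the analysis rule. The word that introduces the outcomes named in section 7.3 makes them examples, so the rule covers cost as a quantitative outcome. Costs driven by length of stay are usually right-skewed, and the rule would then choose the Mann-Whitney test. That test asks whether values in one arm tend to rank above those in the other. A cost comparison asks how much more or less is spent per patient, which is a difference in arithmetic means. The two can disagree when a few patients carry most of the cost, and long critical care stays can produce that pattern.

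**Working it through.** **Outcome definition against data items**

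| Component of the cost outcome (5.4) | What is needed | Where it is listed |
|---|---|---|
| Dose price difference | A fixed price per dose, no patient data | Not needed in the lists |
| Hospital stay | Start and end of stay | Operative day, and actual discharge in 7.1 |
| Critical care stay | Entry to and exit from critical care | No item in 7.1, no row in 5.5 |

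Two of the three components are covered. The third is not listed.

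**The plan's own figures.** The protocol gives no unit cost, so there is no cost figure to reproduce. The one figure used below is the arm size in section 5.6: "Twenty patients in each group are needed based on 80% power for a two-sample t-test". With a difference of 15, SD of 16, two-sided 5% significance and 80% power, the normal approximation gives n = 2 × (1.96 + 0.84)² × (16/15)² ≈ 17.9, so 18 per arm. Allowing for 10% attrition, 18/0.9 = 20. The figure reproduces. The point does not depend on it.

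**What a missing critical care item does to one patient's cost (assumed inputs).** Take a 5-day stay with 1 critical care day, and let that day cost c ward days, with c from 2 to 5.
- True cost in ward-day units: 4 + c, so 6 (c = 2) to 9 (c = 5).
- Cost if every day is priced as a ward day: 5.
- Understatement: 1 − 5/6 = 17% to 1 − 5/9 = 44%.

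This is the error in the cost level of one hypothetical patient. It is not a bias in the between-arm comparison.

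**What the rank test does with skewed costs (assumed inputs).** Take 20 patients per arm, ward days at 400 units and critical care days at 1500. In each arm 10 patients stay 5 days and 10 stay 6 days. In one arm, three of the 6-day patients also have 5 extra critical care days each.
- Mean, first arm: 5.5 × 400 = 2200.
- Mean, second arm: 2200 + (3 × 5 × 1500)/20 = 2200 + 1125 = 3325.
- Difference in means: 1125.
- Medians: 2200 and 2200.
- Hodges-Lehmann shift: 0.
- Mann-Whitney p = 0.66.
- Sample skewness in the second arm: 1.94.

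The rank method reports no shift while the mean cost per patient differs by about half of the first arm's mean (1125/2200 = 51%).

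A simulation of lognormal costs with equal medians of 4000, 20 per arm, gives the same picture. With log-SDs of 0.4 and 0.8, the means differ by 4000 × (exp(0.32) − exp(0.08)) ≈ 1175, and Mann-Whitney rejects in about 6% of trials. With log-SDs of 0.5 and 1.0, the difference is 4000 × (exp(0.5) − exp(0.125)) ≈ 2062, and it rejects in about 6.5%.

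**Precision of a mean difference at this size.** In the 20-per-arm example the SDs are about 205 and 2840. The standard error is √(205²/20 + 2840²/20) ≈ 637. With about 19 degrees of freedom (t = 2.09), the Welch 95% interval is 1125 ± 1332, or about −207 to 2457. It includes zero (p = 0.09), but it states the size of the difference and its uncertainty, which the rank test does not.

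**The case against.** The strongest reply is that an unlisted item is not an uncollected one. The lists in section 7.1 are not exhaustive: gastric volume is a named secondary outcome that is missing from them too, yet it will plainly be measured, since it has a timeline row in section 5.5 and a technique in section 10.8. Post-operative notes and the ERP database are named sources, and outcome data are due at hospital discharge. This stands in part. It rules out the inference that critical care time will not be recorded, or that it would be priced as ward time. It does not remove the gap, because critical care stay, unlike gastric volume, has neither a list item nor a timeline row, and the protocol does not say that these sources hold the times.

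A second reply concerns wording. In the outcome sentence, the word for a difference attaches most naturally to the dose prices, and section 7.3 never names cost. A rank test also does not prevent mean costs from being reported, and an unseen statistical analysis plan may give unit costs and a costing method. All of this is fair. Even so, a between-arm comparison of stay costs is the evident purpose, and the protocol's only rule for such a comparison is unsuited to it. Section 7.3 states that rule outright; it does not leave the choice to the analysis plan.

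Third, the preference in section 5.7 is not an eligibility criterion and carries no proportion. This stands: how often critical care stays will occur is unknown.

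**Conclusion.** The point holds as a minor one. Critical care stay is part of the defined outcome but is not on any data list, and the skewness rule, applied as written, would test skewed costs with a method that does not estimate a cost difference.

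A reader might infer that the cost outcome cannot be produced at all, or that its result would be unusable. The documents do not support that. The dose price is fixed, hospital stay can be costed from the operative day and actual discharge, critical care times may be retrievable from the named sources, and means may be reported alongside a rank test.

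A reader might also take the 17% to 44% as the bias in the trial's cost result. It is not. It rests on an assumed stay, an assumed critical care day and an assumed cost ratio. If critical care use is similar in the randomised arms, much of the error cancels in the comparison. The differences of 1125 to 2062 units likewise rest on assumed costs. They show that the two methods can diverge, not by how much they will.

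This is one secondary outcome of a 40-patient pilot. The sample size and the primary analysis do not depend on it.

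**What to change.** - In section 7.1, post-operative data collection, add date and time of critical care admission and of critical care discharge.
- In section 7.3, take cost out of the skewness rule. State that per-patient cost is compared between arms as a difference in arithmetic means with a bootstrap 95% confidence interval, whatever the skewness.

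The cost is two extra data fields and one sentence of analysis wording. The interval will be wide at about 20 patients per arm, so the result should be read as a pilot estimate. The change is easiest before recruitment starts.

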# 5.5 Participant timeline

	Enrolment	Allocation	Close-out					
TIMEPOINT	Surgical OPD	POAC	Op Day	POD1 & POD2	POD3	POD5	POD7	D/C Hospital
ENROLMENT:								
Eligibility screen	Х							
HbA1C*			Х					
Informed consent		Х						

PQRS score	Х	Х		Х		Х	
Fasting glucose (POCT)	X*						
Allocation	Х						
INTERVENTIONS:							
Preload®		Х					
Generation UCAN		Х					
ASSESSMENTS:							
Baseline Data Collection	Х						
Outcome Data Collection		Х	Х	Х	Х		х
Gastric Volume Measurement		Х					
Blood samples		Х	Х	Х			
Insulin Resistance (HOMA) Calculation	X**	X**	Х	Х			
Hand Grip Strength**	х		х	Х	Х	Х	

\*If a patient has a recent HbA1c result available on the laboratory results system this will be used for screening as opposed to point of care blood glucose.

#### 5.6 Sample Size

The standard deviation for insulin resistance data was obtained from a previous study of pre-operative carbohydrate treatment in total hip replacement surgery (Soop 2001). Twenty patients in each group are needed based on 80% power for a two-sample t-test, detecting a minimal important difference of 15% in change of insulin resistance on the first postoperative day from baseline, with a standard deviation of 16% and a two-tailed significance level of 0.05. A minimal important difference of 25% was used in a previous study comparing pre-operative carbohydrate treatment with a placebo group for patients who had total hip replacement (Soop 2004) . In this study two carbohydrate drinks are being compared, PreLoad with Generation UCAN. Therefore, a smaller minimal important difference of 15% was deemed appropriate. This sample size calculation allows for 10% attrition.

\*\* Measured twice a day first three postoperative days then alternate days until discharge from hospital.

\*\*\*The baseline HOMA to be done on either of these 2 visits as long as the patient is fasted.

#### 5.7 RECRUITMENT

The colorectal specialist nurses will be asked to forward details of patients listed for eligible surgery following each Colorectal Cancer MDT Meeting. All of the surgeons who are part of this group, along with the Waiting List Clerks who book the operation dates, the Pre-operative Assessment Clinic staff (the CI also undertakes weekly Cardiopulmonary Exercise Testing Clinics in this area) and the Enhanced Recovery Nurse will all be aware of the study eligibility criteria and inform the research team as early as possible regarding such patients.

Patients requiring admission to a higher level of care and therefore arterial line monitoring will be preferred due to the ease of blood sampling.

Local data for the past four years indicates an average of 50 eligible patients per year at the Royal Blackburn Hospital. The Royal Surrey County Hospital has a higher volume of eligible patients. Due to the non-invasive nature of the intervention and experience with current interventional RCT at both centres in a similar study population a high approach to consent ratio would be expected. Hence recruitment of 40 patients (20 patients per centre) is feasible in 6 months.

## 6. METHODS: ASSIGNMENT OF INTERVENTIONS

## 6.1 ALLOCATION

Sequence generation:

Patients will be randomised to groups using the online randomisation service (sealed envelope) allowing allocation concealment:

https://www.sealedenvelope.com

Implementation:

The CI and the Clinical Research Fellow will enrol participants and assign participants to interventions.

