## 4.3 TRIAL DESIGN

3

Randomised controlled single-blinded (subject only) parallel group, 1:1 allocation ratio superiority framework study.

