# 5.3 Interventions

Following consent and randomisation at the Preoperative Assessment Clinic (POAC) visit one group will receive the current pre-operative carbohydrate solution, *Preload*® (a maltodextrin solution), and the other group will receive *Generation UCAN* (a hydrothermally modified starch solution) to take home.

In both cases these will be dispensed as a powder in a clear plastic zip lock bag to ensure blinding of the patient (the research team will have decanted the appropriate dose of each supplement into these bags and will be aware of the allocated intervention). This will be a single sachet, in the case of *Preload®*, and an equivalent weighed and measured volume from a large tub, in the case of Generation UCAN. Both groups will be instructed to reconstitute the powder provided in 400mls of water on the day of surgery, and consume it between two and three hours before surgery, as per standard practice in the ERP.

Both groups will also be instructed to consume approximately 500mls (1 pint) of water with their evening meal the evening before surgery to remain well hydrated.

The Control group will receive 47.5g of carbohydrate in the form of Preload®.

The Intervention group will receive 56.55g of flavoured Generation UCAN (providing 47.5g of carbohydrate).

All other aspects of patient care will be standardized as per our ERP (see Appendices).

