## 9.3 Consent

Once the research team are informed about an eligible patient as described in the recruitment section they will meet them at their next hospital attendance & provide them with a written Patient Information Sheet (PIS) and a verbal description of the study along with contact numbers should they wish further information or clarification. They will be followed by telephone in the interim to gauge interest, and again at their preoperative assessment clinical visit to ascertain if they wish to participate. Some patients may be encountered for the first time at this clinic and may be willing to participate after sufficient time to absorb the PIS, which will vary individually. If so, consent will be taken followed by randomisation in order to provide them with their allocated bags of *PreLoad®* or *Generation UCAN* to take home with them to take as directed in the intervention section.

No other aspect of care will be altered apart from that detailed in the study protocol (i.e. provision of different pre-operative drink in intervention arm). The conduct of anaesthesia and planned surgical technique will be at the discretion of the responsible clinicians.

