## 10.2 BLOOD SAMPLING & HOMA CALCULATION OF INSULIN RESISTANCE

#### **BLOOD SAMPLING**

The HbA1C will be collected in an EDTA sample (both centres will analyse these samples using TOSOH HPLC analysers), 1.5mls blood for cortisol in a serum gel tube (both centres will analyse these samples with Advia Centaur analysers), insulin with 5-10ml of blood in a lithium heparin (orange) tube. The insulin samples need to be received in laboratory within 30 minutes, then centrifuged and frozen for transport to Central Manchester Foundation Trust laboratory in the case of Royal Blackburn Hospital. The Royal Surrey County Hospital will perform this test in-house. Both sites use Mercoda insulin ELISA kit. Serum Glucose samples will be collected in a yellow topped tube. Royal Blackburn Hospital uses an Ortho Vitros analyser and the Royal Surrey County Hospital uses Siemens Advia. However external proficiency testing data shows that on average the methods perform within 2.5% of each other, which is acceptable.

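### Neither the allocation nor the primary comparison accounts for centre, although two centres with different laboratories each contribute about half of 40 patients

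*Protocol*

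**What the plan says.** The design (4.3) is a "parallel group, 1:1 allocation ratio superiority framework study". On generating the sequence, section 6.1 says "Patients will be randomised to groups using the online randomisation service (sealed envelope) allowing allocation concealment". Neither there nor elsewhere does the protocol mention stratification, blocking or minimisation. Section 6.1 adds that the chief investigator and the research fellow both enrol and assign participants. Section 5.3 says the research team knows the allocated drink.

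Section 5.7 concludes: "Hence recruitment of 40 patients (20 patients per centre) is feasible in 6 months". Section 5.6 sets the size: "Twenty patients in each group are needed based on 80% power for a two-sample t-test", for a 15% difference, SD 16% and two-sided 5% significance, with 10% attrition allowed for.

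The blood sampling appendix shows that the measurement chain depends on centre. Insulin from one hospital is frozen and sent to an outside laboratory; for the other, "The Royal Surrey County Hospital will perform this test in-house". For glucose, "Royal Blackburn Hospital uses an Ortho Vitros analyser and the Royal Surrey County Hospital uses Siemens Advia". The same appendix says that both sites use the same insulin kit and that the glucose methods agree within 2.5% on average. It gives no such agreement figure for insulin.

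Section 7.3 compares change in insulin resistance at POD 1 by an independent-samples t-test or a Mann-Whitney U test, depending on skewness. Regression adjustment follows only if differences are seen in prognostic baseline demographic or clinical variables. Centre is not named.

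**The concern.** Centre is known before randomisation. In this trial it determines where and how one of the two HOMA inputs is assayed and which analyser measures the other. If the outcome differs between centres for any reason, two things follow from a plan that ignores centre. A chance excess of one centre in one arm moves the estimated treatment difference. The between-centre spread also stays in the error term of the unadjusted test. With 40 patients, uneven splits are common, and the sample size leaves no spare power to absorb the loss.

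Stratification cannot be left until later. It must be set in the randomisation service before the first patient, and the allocation section is where a protocol states it.

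**Working it through.** **Inputs.** From section 5.6: target difference 15, SD 16, two-sided alpha 0.05, power 80%, attrition 10%, 20 per arm. From section 5.7: 20 patients per centre. The protocol gives no centre difference in outcome, so 8 and 16 points (0.5 and 1 SD) are assumptions chosen to show a range.

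**1. The plan's own figure.** n per arm = 2 × (1.96 + 0.8416)² × 16² / 15² = 17.9, so 18. With attrition, 18 / 0.9 = 20 per arm, as stated. The calculation has no term for centre. By the noncentral t, 18 evaluable per arm gives 78.0% power.

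**2. Chance imbalance.** With 20 per arm and 20 per centre but no stratification, the number X from one centre in one arm is hypergeometric: P(X = x) = C(20,x) × C(20,20−x) / C(40,20).

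| Split within a centre | Probability of that or worse |
|---|---|
| 12:8 | 34.3% |
| 13:7 | 11.3% |
| 14:6 | 2.6% |

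Under simple randomisation, where arm totals also vary, the arms differ by at least 20 percentage points in their share of one centre with probability 27%, and by at least 30 points with probability 8%.

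**3. Shift in the estimate.** Shift = difference between arms in centre share × centre difference in outcome. A 12:8 split means shares of 12/20 and 8/20, a difference of 0.20; 13:7 gives 0.30.

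| Split | 8-point centre difference | 16-point centre difference |
|---|---|---|
| 12:8 | 1.6 (11% of 15) | 3.2 (21% of 15) |
| 13:7 | 2.4 (16% of 15) | 4.8 (32% of 15) |

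Imbalance is equally likely in either direction, so the expected shift is zero.

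**4. Power at 36 evaluable patients.** With equal centres, a centre difference D adds D²/4 to the variance seen by an unadjusted test.

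- D = 8: variance 256 + 16 = 272, SD 16.5, noncentral t power 75.5%.
- D = 16: variance 256 + 64 = 320, SD 17.9, noncentral t power 68.6%.

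Simulation (8,000 trials per scenario, residual SD 16, true difference 15) agrees. The unstratified rows have fixed arm sizes.

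| Allocation and analysis | D = 0 | D = 8 | D = 16 |
|---|---|---|---|
| Unstratified, unadjusted | 77% | 75% | 68% |
| Unstratified, centre in model | 76% | 76% | 76% |
| Stratified, unadjusted | 78% | 76% | 70% |
| Stratified, centre in model | 78% | 78% | 78% |

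Type I error is 4.8% to 5.3% in the first row and 4.9% in the last. Stratifying and then testing without centre gives 2.9% at D = 16: the test becomes conservative because its error term keeps a spread that the design has removed.

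**The case against.** The strongest reply is that section 6.1 is silent and does not rule stratification out, that covariates are ordinary material for an analysis plan not shown here, and that any centre effect is conjecture. Much of this stands.

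- **Silence.** The service may already be set to stratify by centre. If so, one sentence closes half the point.
- **Where the gain lies.** Most of it comes from adjustment. At 16 points, adding centre to the model without stratifying raises power from 68% to 76%; stratification adds about two points more. However, section 7.3 itself fixes an unadjusted primary test and makes adjustment depend on an observed imbalance, so the protocol has not simply left the matter open.
- **Size of the centre effect.** The insulin kit is shared and the glucose methods agree closely on average. A constant assay offset cancels in change from baseline, and a proportional one cancels if change is expressed as a percentage of baseline. At 8 points the loss is only two or three percentage points of power.
- **The 20 per centre** is a recruitment projection. The 34% applies only to fixed 20/20 margins.

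A reader might infer that the result would be biased, or that a drug-like effect of the drink could not be told apart from a centre effect. Neither follows. The expected shift is zero, type I error stays near 5%, and centre is recorded for every patient, so regression can separate the two even after an uneven split.

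A reader might also infer that anaesthetic or recovery practice differs between the hospitals, because section 9.3 says "The conduct of anaesthesia and planned surgical technique will be at the discretion of the responsible clinicians" while section 5.3 says "All other aspects of patient care will be standardized as per our ERP". The discretion is general and no section says it is used differently by centre. The protocol gives one enhanced recovery programme, one set of discharge criteria and one set of morbidity definitions.

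**Conclusion.** The point holds as one of precision. As written, centre enters neither the allocation nor the primary comparison, although the centres use different insulin laboratories, sample handling and glucose analysers. If margins are 20/20, a 12:8 split or worse has a 34% chance. A 12:8 split moves the estimate by 1.6 to 3.2 points for assumed centre differences of 8 to 16 points. Accounting for centre in both design and analysis recovers two or three percentage points of power at 8 points and about ten at 16. The upper figure rests on a full-SD centre difference, for which the documents give no evidence. The case for change is that the remedy costs almost nothing and that stratification cannot be added once recruitment is under way.

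**What to change.** - **Section 6.1:** state that randomisation is stratified by centre, using permuted blocks of randomly varying size that are concealed from the enrolling staff. Varying sizes matter because those staff know past allocations and could predict the end of a fixed block. If the service is already set this way, say so.
- **Section 7.3:** include centre as a prespecified factor in the primary comparison, whether or not a baseline imbalance is seen. A linear model with arm and centre would serve, or a centre-stratified rank test if the data are skewed.

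Both changes are needed: stratification without adjustment gives only 70% power at a 16-point centre difference. The cost is one setting in the randomisation service, protocol wording and one degree of freedom. The sample size stays at 20 per arm.
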